Background/Rationale: In September 2015 the EMPA-REG trial presented data on positive effects of empagliflozin, a SGLT-2 inhibitor on CV outcomes. This has created a need for data on how this class of medicines affect CV event rates when used in clinical practice. An observational study can never replicate a randomized controlled trial (RCT) since neither placebo treatment nor randomisation is part of clinical practice. An observational study will instead use an active comparator group. To provide a good comparison, the treatment arms should have ideally exchangeable treatment alternatives, similar patient characteristics and baseline risk of the outcome. For medication classes recently introduced on the market, such as the SGLT-2 inhibitors, it may be difficult to find a suitable comparator and the number of patients exposed and length of exposure may be limited. Therefore this study has two steps where step 2 is described in this amendment. Step 1 assesses the number of patients initiating use with this class of medicines and their length of follow up as well as describes characteristics of new users of SGLT-2i and potential comparator groups. Step 1 is now completed and shows that a suitable comparator group can be identified and that there is sufficient statistical power to conduct a comparative analysis of the outcomes of interest (Step 2). This step is described in this amendment.

Objectives and Hypotheses: The primary aim of this study is to compare the risk for hospitalization for heart failure, inpatients with T2DM who are new users of a SGLT-2 inhibitor versus an active comparison group including patients with T2DM who are new users of other glucose lowering drugs (GLD). A secondary aim is to compare all-cause mortality using similar methods. Exploratory aims are to estimate the incidence of acute myocardial infarction and atrial fibrillation in both treatment groups.

Methods:

Study design: Cohort study (Section 3.1)

Data Source(s): In the UK CPRD, THIN; in the US Humedica, MarketScan; in Sweden the DAISY database; in Norway the DAPHNE database and in Denmark the DAFFODIL database; in Germany (“Diabetes Patientenverlaufsdokumentation” [DPV]) and Manitoba Centre for Health Care Policy (MCHP) in Canada (Section 3.1.1)

Study Population: New users of SGLT-2i and other GLD respectively (Section 3.2)

Exposure(s): SGLT-2i and other GLD (Section 4.1)

Outcome(s): Hospitalization for heart failure, all-cause mortality (only possible in UK and the Nordic countries), acute myocardial infarction and atrial fibrillation respectively. (Section 4.2)

Sample Size Estimations: The primary endpoint will be hospitalization for heart failure. A risk reduction in this endpoint of 20% for the SGLT-2i group compared to the control group will be considered clinically meaningful. For 85% power to detect a risk reduction of 20% with a two-sided alpha level of 0.05, and up to 1:3 treatment allocation of SGLT-2i to the comparator arm, a total of 970 events will be needed across both treatment groups and all databases after the matched SGLT-2i and control groups have been created. This calculation assumes the background rate of hospitalization for heart failure in the standard of care group is 0.625 events per 100 person-years. For 1:3 treatment allocation, approximately 40,842 person-years will be needed in the SGLT-2i group and 122,526 person-years will be needed in the control group. However, the key driver for the power and the analysis is the number of events. The sample size is merely an approximation of how many person-years might produce the required number of events based on the assumed event rates. Also, the ratio of SGLT-2i: control matching may vary across the databases but as long as a total of 970 events are achieved, the analysis will be sufficiently powered.

The background rate of 0.625 events per 100 person-years is relevant for US, UK and Germany based on literature and empirical rates from the databases included in the study. Based on Swedish data, a substantially higher rate of 1.58 events per 100 person years has been observed. This difference in rates could be due to the age distribution and other factors including case ascertainment and baseline cardiovascular risk.

As there may not be enough statistical power for a standalone analysis in any of the individual country databases, a meta-analysis approach will be used to conduct the treatment comparison by pooling the hazard ratio estimates from all of the databases assuming that a total of 970 events have been observed. The higher rate of 1.58 events per 100 person years may apply in Sweden and the other Nordic countries. This higher event rate allows for the possibility of a sufficiently powered analysis in the Nordics alone. If 970 events have been observed in the Nordics, then a separate analysis will be submitted for the Nordics database. Assuming 1:3 matching, approximately 16,019 person-years will be needed in the SGLT-2i group and 48,054 person-years will be needed in the control group to obtain the target of 970 events.

Statistical Analysis: The primary objective of step 2 is to compare the incidence of heart failure hospitalization between new users of SGLT-2 inhibitors and the comparator arm using a hazard ratio (relative risk) and corresponding 95% confidence interval. The analysis will be performed using the Cox proportional hazards model or some other

appropriate method. The secondary endpoint of interest, (all-cause mortality), will also be compared between the SGLT-2i group and comparator arm using a similar statistical method. In addition, the exploratory outcomes, the baseline characteristics and other clinical parameters for each treatment group will be summarized descriptively. Matching by propensity scores will be used to balance the potential confounding covariates between the SGLT-2i group and the reference group to ensure that the two groups are as similar as possible at baseline. This is described in Section 5. To achieve sufficient power, a meta-analysis based on the DerSimonian-Laird random effects model will be applied to integrate the point estimates from each of the individual database analyses and calculate an overall weighted estimate and corresponding 95% CI [6]. A standalone analysis may be implemented in the Nordics database assuming that a total of 970 events have been observed.

AMENDMENT HISTORY

Date	Brief description of change	Administrative Change / Amendment / New Protocol Version.
April 12, 2016	Amendment describing the analyses in Step 2	Amendment
Protocol revised August 18	Inclusion of additional countries (Norway, Denmark, Germany and Canada) and incorporating suggestions from the external Publication Steering Committee	New Amendment Version
Protocol revised October 26	Including suggestions from the external Publication Steering Committee. Adjusted based on data availability and estimates of background rates.	New Amended Version
Revised protocol November 22	Including suggestions from MARC and GPT review and updates from countries and databases.	New Amended Version

MILESTONES

Date	Milestone
Q4 2015	Development of Study Concept Sheet
Q4 2015	Final Protocol
November 17 2015	Development of Study Concept Sheet
December 16 2015	Internal scientific review of protocol
December 31 2015	Approval of protocol
	Database/EC/IRB approvals
June, 2016	– CPRD+THIN (ISAC and SRC approval Step 1)
	Core data sets set up
May 4, 2016	– THIN
February 28, 2016	– Humedica
April 30, 2016	– MarketScan
February 15, 2016	– Sweden
	Final results tables step 1
September, 2016	– CPRD+THIN
July 31, 2016	– Humedica
March 31, 2016	– MarketScan
November, 2016	– Update Sweden
November, 2016	– Denmark
November, 2016	– Norway
September 15, 2016	– Germany
	– Canada
	Abstract and publication step 1
October 15	– Abstract draft
November	– Abstract submitted
January 2017	– Manuscript first draft
February 2017	– Manuscript submitted
	Step 2 results comparative analysis
January, 2017	CPRD/THIN (ISAC/SRC subm. step 2 Sep16. Awaiting free text. ISAC approval pending)
July 31, 2016	Humedica
May 13, 2016	MarketScan
December, 2015	Sweden
November 1, 2016	Germany
February, 2017	Canada
	Step 2 combined comparative analysis of risk
December 10, 2016	All databases combined in meta-analysis
December 15, 2016	Abstract draft
December 20, 2016	Abstract submitted

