2. OBJECTIVES AND HYPOTHESES

2.1 Primary Objective(s) & Hypothesis(es)

This study has been divided in two steps where step 1 has assessed the study population length and follow up as well as comparability between SGLT-2i users and users of other diabetes medication groups. The objectives of step 1 are described in the full protocol (D1690R00015). This amendment concerns step 2 which is a comparative analysis of the risk for CV events between SGLT-2i users and a group of active comparators.

Step 2 has one primary, one secondary and two exploratory objectives and will only be conducted given that a comparative analysis is feasible based on the results from step 1. Feasibility was determined by the following requirements a) the study population has enough length of follow up, required variables of interest, and size to have sufficient power to assess the outcome of interest according to the power calculations presented in Section 5.3 and b) a suitable comparator group. Suitability of comparator groups was assessed based on the propensity score matching by applying normal requirements to assess sufficient match between different groups. This process will be outlined in more detail in the statistical analysis plan (SAP). Step 1 also informed whether analysis needed to be done on SGLT-2i class level or dapagliflozin separately applying the above-mentioned criteria. As step 2 is considered feasible based on the criteria, this protocol amendment outlines the analysis including the specifics about the treatment group, comparator group, and primary outcome, for this step. The primary, secondary and explorative objectives of the study amendment (step 2) are:

Primary objective

To compare the risk for hospitalization for heart failure between patients with T2DM who are new users of SGLT-2 inhibitors as a class versus an active comparison group including patients with T2DM who are new users of other GLD.

Secondary objective

To compare all-cause mortality between patients with T2DM who are new users of SGLT-2 inhibitors as a class versus an active comparison group including patients with T2DM who are new users of other GLD. Due to data availability this objective can only be addressed in UK and the Nordic countries.

Exploratory objectives

To estimate the incidence of acute myocardial infarction and atrial fibrillation respectively in new users of SGLT2 inhibitors and of other GLD.

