5.3 Sample Size and Power Calculations

Power calculations

The primary endpoint will be hospitalization for heart failure. A risk reduction in this endpoint of 20% for the SGLT-2i group compared to the control group will be considered clinically meaningful. For 85% power to detect a risk reduction of 20% with a two-sided alpha level of 0.05, and up to 1:3 treatment allocation of SGLT-2i to the comparator arm, a total of 970 events will be needed across both treatment groups and all databases after the matched SGLT-2i and control groups have been created (Table 1). This calculation assumes the background rate of hospitalization for heart failure in the standard of care group is 0.625 events per 100 person-years and assuming a 20% reduction a rate of 0.5 events per 100 person years in the SGLT-2i group. For 1:3 treatment allocation, approximately 40,842 person-years will be needed in the SGLT-2i group and 122,526 person-years will be needed in the control group. However, the key driver for the power and the analysis is the number of events. The sample size is merely an approximation of how many person-years might produce the required number of events based on the assumed event rates. Also, the ratio of SGLT-2i: control matching may vary across the databases but as long as a total of 970 events are achieved, the analysis will be sufficiently powered.

The background rate of 0.625 events per 100 person-years is relevant for US, UK and Germany based on literature and empirical rates from the databases included in the study. Based on Swedish data, a substantially higher rate of 1.58 events per 100 person years has been observed. This difference in rates could be due to the age distribution and other factors including case ascertainment and baseline cardiovascular risk.

As there may not be enough statistical power for a standalone analysis in any of the individual country databases, a meta-analysis approach will be used to conduct the treatment comparison by pooling the hazard ratio estimates from all of the databases assuming that a total of 970 events have been observed. The higher rate of 1.58 events per 100 person years may apply in Sweden and the other Nordic countries. This higher event rate allows for the possibility of a sufficiently powered analysis in the Nordics alone. If 970 events have been observed in the Nordics, then a separate analysis will be submitted

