6. STUDY CONDUCT AND REGULATORY DETAILS

6.1 Data Management

6.1.1 Study Flow Chart and Plan

This study will be carried out internally to the largest extent possible. We will utilize the internal AZ access to Humedica. Combining THIN and CPRD data requires the analysis to be conducted by a contractor (CEIFE). The MarketScan data are analyzed by the Truven Health analytics.

The Swedish and Danish data (DAISY and DAFFODIL) will be updated with data on hospitalization diagnoses for 2015 which will be available in Q4 2016. Norwegian data (DAPHNE) is currently waiting to be delivered, estimated to November 2016. The Nordic/Baltic MC has access to all these databases and will conduct the analyses. The German data (DPV) will be updated quarterly and the Q2 2016 data will be available September 2016.

The Canadian data will be received from The Manitoba Centre for Health Policy (MCHP), in Q4 2016 for part 1 and Q2 2017 for part 2. These data will be analyzed by researchers at the University of Manitoba and Seven Oaks Hospital, and not internally at AZ Canada.

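### The milestones contradict the analysis definition: the all-database meta-analysis is dated before the UK and Canadian step 2 results that it is meant to contain

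*Combined protocol and SAP*

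**What the plan says.** The step 2 entries in the Milestones table put the combined analysis, described as "All databases combined in meta-analysis", at "December 10, 2016". An abstract draft follows on 15 December and its submission on "December 20, 2016".

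The database-level step 2 results in the same table are dated as follows:

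- Sweden: December 2015
- MarketScan: 13 May 2016
- Humedica: 31 July 2016
- Germany: 1 November 2016
- UK: January 2017, entered as "CPRD/THIN (ISAC/SRC subm. step 2 Sep16. Awaiting free text. ISAC approval pending"
- Canada: February 2017
- Denmark and Norway: no step 2 date

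Section 6.1.1 gives another date for Canada: data are to arrive "in Q4 2016 for part 1 and Q2 2017 for part 2".

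On content, section 5.3 describes the treatment comparison as "pooling the hazard ratio estimates from all of the databases assuming that a total of 970 events have been observed". Section 3.1.1 rests the feasibility of both meta-analyses on exposure time from every country. Sections 3.1 and 3.1.1 name the UK and Canada as study sources. On all-cause mortality, section 2.1 states: "Due to data availability this objective can only be addressed in UK and the Nordic countries".

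**The concern.** The date of the pool decides which data enter the primary estimate, so this is more than a clerical matter. If the schedule is followed, the pooled heart failure result will lack databases that the plan says it contains. If the UK and Canada are added later, the same endpoint will have been pooled twice, and no text says which result is primary. That choice would then be made with the first result known.

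The two pools need not agree closely. Under the DerSimonian-Laird model the between-country variance is re-estimated when countries are added, so every country's weight can change.

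Mortality is more exposed because fewer sources can supply it. The UK is the only one outside the Nordic region, and Appendix 1 takes its mortality rate for the power calculation from CPRD, one of the sources that would be absent.

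**Working it through.** **The plan's own figure.** The target is 970 events (85% power, hazard ratio 0.80, two-sided alpha 0.05, 1:3 allocation). Schoenfeld's formula gives (1.960 + 1.036)² / [0.25 × 0.75 × (ln 0.80)²] = 962, within 1% of 970. Person-years: 970 / (0.005 + 3 × 0.00625) = 40,842 for SGLT-2i and 3 times that, 122,526, for controls, as stated. The target is therefore not in dispute. It fixes how many events are needed, not which databases supply them.

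**Date order.** Each gap is the source date minus 10 December 2016. Where only a month or quarter is given, its first and last days are used.

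| Source | Date in the plan | Days after the pool |
|---|---|---|
| UK (CPRD/THIN) | January 2017 (Milestones) | 22 to 52 |
| Canada | February 2017 (Milestones) | 53 to 80 |
| Canada, part 2 | Q2 2017 (section 6.1.1) | 112 to 202 |

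The abstract submission on 20 December is 10 days after the pool. It therefore still precedes the UK results by at least 22 − 10 = 12 days and the Canadian results by at least 53 − 10 = 43 days.

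The two Canadian dates also conflict, on the reading that part 2 in section 6.1.1 means step 2: results in February 2017 cannot come from data received in April 2017 or later.

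**Coverage on 10 December 2016.**

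- Heart failure: seven countries are named (US, UK, Sweden, Denmark, Norway, Germany, Canada). Without the UK and Canada, at most 7 − 2 = 5 remain. Only the US, Sweden and Germany have a step 2 date before the pool.
- Mortality: four countries can contribute (UK, Sweden, Denmark, Norway). Without the UK, at most 4 − 1 = 3 remain. Three is the best case: Denmark and Norway have no step 2 date, and section 6.1.1 still expected the Norwegian delivery in November 2016.

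**Text that might resolve the conflict.** The second phase in section 3.1 concerns additional countries, not two already named. Sections 5.1 and 5.1.1 describe a single pooling step per endpoint. No text calls the December pool interim, partial or preliminary, or says how it would be updated.

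**The case against.** The strongest reply is that this is a stale table, not a decision to pool early. There is support for that. Sweden's step 2 results are dated December 2015, before its core data set (15 February 2016), Canada's step 1 date is blank, and the Canadian step 2 dates disagree. The documents do not show which entry is wrong, the December date or the all-database label. This stands: the supported finding is that the dates and the definition cannot both hold, not that the sponsor chose a partial pool.

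A second reply is that the December entries lead only to an abstract, while section 6.3.1 ties the full report to completion of the final analytic dataset. This also stands in part: the final report need not omit the UK or Canada. But section 6.3.1 does not say which pool is primary, so the gap remains.

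A reader might infer two stronger conclusions, and the documents support neither:

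- **Loss of power.** Section 5.3 ties power to 970 events, and the remaining countries might reach that number. No event counts by database are given, so a loss cannot be shown or sized.
- **An inflated false-positive rate from testing twice.** No text plans a second pool or a test of both. Any figure would need assumed information fractions, and the usual formula for correlated looks does not strictly apply when random-effects weights are re-estimated.

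**Conclusion.** The contradiction holds and follows from the stated dates alone. A pool run on 10 December 2016 could not contain two of the seven named countries, and its mortality analysis would rest on at most the three Nordic countries. The result would not be the all-database estimate that the plan defines, and nothing marks it as anything less. The conclusion assumes only that the UK and Canadian result dates mean what they say. It concerns database coverage and the identity of the primary result. It does not extend to power or type I error, and it does not establish that the final report would be incomplete.

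**What to change.** 1. Reconcile the Milestones table with sections 3.1.1, 5.1 and 5.3. Settle the two Canadian dates in the table and in section 6.1.1, and enter step 2 dates for Denmark and Norway.
2. Keep the all-database definition. Run the primary pool once for heart failure hospitalization and once for mortality, after the last listed database able to contribute to that endpoint has delivered.
3. If a December 2016 pool is still wanted for the abstract, label it preliminary, list the databases that it contains for each endpoint, and state in advance that the full pool is the primary result whatever the preliminary one shows.

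Declaring the December pool primary instead would not be a simple repair, because it would contradict the all-database definition in the synopsis and section 5.3 and the all-country wording in section 3.1.1.

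The drafting cost is a corrected table and a few sentences in section 5.1.1. The real cost is a later heart failure result: February 2017 at the earliest on the Milestones date for Canada, or the second quarter of 2017 on the section 6.1.1 date. Mortality waits for the UK, January 2017 at the earliest, and for the Nordic countries without a date.

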1. BACKGROUND AND RATIONALE

1.1 Rationale for the amendment

In September 2015 the EMPA-REG trial presented data on positive effects of empagliflozin, a SGLT-2 inhibitor on CV outcomes. [1] This has created a need for data on how this class of medicines affect CV event rates when used in clinical practice. An observational study cannot replicate the design and results of a placebo-controlled randomized clinical trial since neither randomisation nor placebo treatment are part of clinical practice. An observational study will need to compare against an active comparator and disease severity as well as prescriber preferences influence the choice of treatment. This may introduce differences in patient characteristics associated with the treatment choice as well as the outcome and is referred to as confounding by indication or channeling bias. The choice of comparator in observational studies requires careful selection and consideration in order to find a comparator with as similar patient characteristics regarding demographics and disease progression as possible. Patients with T2DM include a large span of disease severity which is important to account for; one marker of this is insulin use. As seen in the EMPA-REG population insulin use is common in T2DM patients with established CVD [1]. The SGLT-2i class is relatively recently introduced on the market in both Europe and the US, introduced in November 2012 and March 2013, respectively. Thus both the number of patients exposed to this class of drugs and their follow up time on the medicines are limited.

This protocol amendment concerns the second step (Step 2) of the study. The rationale for conducting the first step (step 1) descriptive study was to gain more insight into the patient characteristics of patients at high baseline CV risk initiating use with SGLT-2i, and specifically dapagliflozin, and four potential comparator groups (DPP-4i, SU, GLP-1ra and a group containing all other glucose lowering drugs (GLD) except SGLT-2 inhibitors) in different countries (United States (US), United Kingdom (UK), Sweden, Denmark, Norway, Germany and Canada). Further, since SGLT-2i were recently marketed little is known on the patient characteristics in general of users of these medications in comparison with patient characteristics of users of other medication classes. It is likely that they differ since SGLT-2i have primarily been recommended as third line treatment in many countries. Previous studies have reported some differences in patient characteristics between new users of DPP-4 inhibitors compared to SU concerning age, diabetes duration and concomitant medication use [2-5]. More differences have been reported between SU users and GLP-1ra users in age, treatment duration and concomitant medications used [3]. This stresses the importance to assess several potential comparator groups to find a suitable comparison group.

The results from the first part of this study (step 1) are descriptive and inform whether it will be feasible to conduct a comparative effectiveness study, assessing the effects of SGLT-2i versus an active comparator, on CV and mortality outcomes (step 2). This study will require adequate power and comparator as well as relevant data for cohort selection and outcomes and to perform required statistical modeling to address channeling bias.

A comparative effectiveness study could fill a current knowledge gap for SGLT-2i as a class in light of the result from the first SGLT-2 inhibitor CV outcomes trial [1].

The study design of the step 2 i.e. this protocol amendment is presented here.

